5.1. STUDY SETTING

This feasibility study involves four diverse hospitals in Bradford, Leeds, Hull and Calderdale which are our intervention sites. We will also recruit four sites that will act as our 'control' to determine if it is possible to collect data from a non-intervention arm. The selection of sites considered population profiles, organisation size and access. We have established support from senior management and will work with the CRN to support coordination. Appropriate site training (in-person or online as preferred) will be provided.

5.2. DATA COLLECTION

5.2.1 Methods of data collection

This feasibility study will utilise a multi-methods approach guided by the Systems Engineering Initiative for Patient Safety (SEIPS) 3.0 Framework (Carayon et al. 2020) across the data collection phase.

5.2.1.1 Intervention arm delivery

This will involve the clinical team identifying suitable participants and research nurses consenting participants and administering a patient survey to collect baseline characteristics data. This phase will also include clinical teams providing older people with materials to help them manage their medicines (e.g., family carer packs and medicine management checklists). As part of our intervention implementation guide, we have developed a customised eight-step checklist to support delivery. Staff will be asked to complete this checklist, and we will use it, along with other data sources such as patient-reported and community pharmacy-reported information, to ascertain the level of fidelity. We will calculate the percentage of intervention each participant receives and use this to establish our progression criteria for future definitive trials (intervention delivery >50% on the fidelity rating scale). We will also use this information to further refine the intervention and implementation guide.

[figure not shown]
In addition, as part of the intervention arm delivery, the research team will administer questionnaires two (2) weeks after discharge to collect data on five (5) outcome measures (PREM1, EQ5D5L, healthcare utilisation, adherence, self-efficacy, and medicines-related problems (MRPs). Depending on the participants' preferences, these questionnaires will be administered either by post, telephone, or online (via a link provided to MS Forms).

Furthermore, the research team will administer a PREM 2 questionnaire (Appendix 9) and collect data on the five outcome measures from the same sample 3 months post-discharge. These questionnaires will be administered via post, telephone or online (Microsoft Teams or Zoom). Below is a flowchart illustrating the patient journey through the project/intervention.

As part of this feasibility study, we will explore what routine data can be collected, with the participants' consent, to aid with our analysis. Presently, we envisage that this will be routinely data about the participant's number of hospital readmissions and data from community pharmacy reporting systems about whether the Discharge Medicine Service was delivered to the participant.

My Medicines Journey: Assessing the feasibility and implementation of a Toolkit

My Medicines Journey: Assessing the feasibility and implementation of a Toolkit

5.2.1.2 Control arm delivery

In addition to the intervention group, the clinical/ research team will recruit 84 older people to form the control group. This sample will be asked to complete patient surveys at the same time points, including PREMs, EQ5D5L, baseline data, healthcare utilisation, adherence, self-efficacy, and MRPs.

5.2.1.3 Assessment of feasibility

To evaluate the feasibility of the intervention, we will use various data collection methods. Along with the patient surveys above, our research team will conduct an online survey using a questionnaire (Appendix 12) with a maximum of 30 hospital staff members.

We will also undertake document analysis of intervention manuals to see if staff have completed the required details and conduct staff observations at various times over 8 weeks at each site. We will request ward-level permission to observe staff members delivering the intervention at the point of delivery. This will help us understand how the toolkit is being implemented and the overall care context in which the intervention is implemented. We will collect focused and general observation data using a structured observation tool or checklist (Appendix 13) and take field notes.

Additionally, we will invite up to 12 hospital staff members and up to 20 older people/carers to take part in semi-structured interviews. These interviews will be conducted face-to-face or online (via Microsoft Teams or Zoom) depending on the participants' convenience and will be facilitated by the research team. The interview topic guides for hospital staff and older people have been included as Appendices 10 and 11, respectively. Interviews will be audio recorded with consent, and anonymised transcripts will be produced from the recording. The analysis will use the framework method to help us explore the experiences, barriers, and facilitators of intervention use.

5.2.2 Data Analysis

We will provide an in-depth understanding of how usable and acceptable the intervention is in practice, as well as barriers and facilitators to delivery underpinned by the SEIPS 3.0 framework. Qualitative data will be analysed using the Framework method (Gale et al., 2013). Descriptive statistics will be employed to analyse survey data. The findings from the study will be used to refine the outcome measures and inform a multi-site trial protocol.

Following our analysis, we will hold dissemination workshops with key stakeholders from the participating organisations. We will present our findings and encourage stakeholders to suggest ways to overcome any challenges or refine our intervention in preparation for a future trial (if indicated from the progression criteria).

5.3 STATISTICS AND DATA ANALYSIS

5.3.1 Sample size calculation

We plan to recruit a diverse sample of 168 older people across 4 intervention sites and 4 control sites during hospital admission, plus hospital staff involved in delivering the intervention across the sites.

There are four varying sample size estimates for this study:

My Medicines Journey: Assessing the feasibility and implementation of a Toolkit

- A. To determine feasibility against the progression criteria (n=84 intervention participants) The sample size is based on the need to understand whether it is possible to consistently recruit 2 participants a week for up to 16 weeks per site and account for attrition. Based on previous feasibility studies, such as Teare et al. (2014) who determined that 70 measurable subjects are required when outcomes are continuous, we believe this is an appropriate sample size to determine feasibility against our progression criteria.
- B. To determine if data can be collected from a 'control' arm (n=84 control participants) Sample size is determined based on A, and contributes to C.
- C. To validate the PREM (n=168 patient participants)

 For validation studies, a widely used rule of thumb suggests 10 responses per item in the instrument.

The PREM contains 15 to 18 items, leading to a sample size in the range of 150 to 180.

The intended sample size is 168.

If this is achieved, the margin of error (for responses to each item) will be:

- A) +/- 7.5% assuming a proportion of 50% at the 95% confidence level
- B) +/- 5% assuming a proportion of 50% at the 80% confidence level

We consider this to be acceptable.

Extreme responses to the items (proportions higher or lower than 50%) will reduce the margin of error.

D. To collect in-depth qualitative data from a smaller sample of patient and staff participants (n=12-30 depending on methods)

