This feasibility study aims to test if the pharmacy team can incorporate the intervention into their regular work, assess the positive and negative impacts of doing so, and determine whether progression criteria (see page 24 for more details) are met, which would indicate a move to full trial. We will ask four NHS sites, including Bradford Teaching Hospitals NHS Trust, Hull University Teaching Hospitals NHS Trust, Leeds Teaching Hospitals NHS Trust, and Calderdale and Huddersfield NHS Trust, to each recruit approximately 21 older people over a span of 12-16 weeks period, which averages out to approximately 2 older people per week (n= 84), but with attrition, we predict a smaller final sample size. Based on previous feasibility studies, such as Teare et al. (2014) who determined that 70 measurable subjects are required when outcomes are continuous, we believe this is an appropriate sample size to determine feasibility.

We will also conduct observations with the team, distribute staff questionnaires, and conduct semi-structured interviews with individuals who have used the intervention.

In summary, phase two of the study will involve:

- Administering the PREM questionnaire, developed in phase one, to assess postdischarge medicine experiences with older people, carers, and health professionals and to test its usefulness.
- We will work with approximately 4 local hospitals and participants' community
 pharmacists to use our Toolkit with older people and their carers. We will assess how
 well it works and its acceptability by using questionnaires, observations and
 interviews. In addition, we shall work with 4 other local hospitals to recruit a control
 group that will be asked to complete patient surveys, including PREMs, EQ5D5L,
 baseline data, healthcare utilisation, adherence, self-efficacy, and DRPs.
- Finally, we will use the findings to enhance the intervention Toolkit and implementation strategy and develop a proposal for a large-scale multi-site trial.

The workflow chart below summarises all components of the study design for the second phase of my medicines journey project.

My Medicines Journey: Assessing the feasibility and implementation of a Toolkit

Study set-up

PREM Refinement

Site recruitment (4 sites for the intervention group and 4 sites for the control group)

Participant recruitment [168 older people, 84 for the intervention arm (21 per site) and 84 for the control group (21 per site)]

Intervention arm delivery

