5.3.3 Statistical Analysis Plan

5.3.3.1 Analysis of the reliability and validity of the PREMs

- We will conduct initial analyses in SPSS to check for normality, outliers, and missing values.
- Our goal is to assess the validity and reliability of the two PREMS. This will involve exploratory factor analysis, a reliability test (Cronbach's alpha coefficient), and a construct validity test.
- We will evaluate the reliability of the PREMs using the composite reliability values for each dimension.

My Medicines Journey: Assessing the feasibility and implementation of a Toolkit

- To assess reliability, we will test for internal consistency using Cronbach's alpha coefficient.
- To determine construct validity, we will examine convergent, discriminant, and predictive validity using a Student's t-test, correction and regression analysis, and an analysis of covariance.

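### Section 5.3.1 C sizes one PREM of 15 to 18 items, but two are validated: 168 recruits cannot give the 18-item PREM 1 ten responses per item, and neither PREM has an allowance for non-return

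*Protocol*

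**What the plan says.** Protocol section 5.3.1 counts people at enrolment: "We plan to recruit a diverse sample of 168 older people across 4 intervention sites and 4 control sites during hospital admission". Estimate C then uses the same figure for the questionnaire: "To validate the PREM (n=168 patient participants"). Its justification is a rule about answers received: "For validation studies, a widely used rule of thumb suggests 10 responses per item in the instrument". The rule is applied once: "The PREM contains 15 to 18 items, leading to a sample size in the range of 150 to 180". On condition that 168 is achieved, C gives a per-item margin of error of plus or minus "7.5% assuming a proportion of 50% at the 95% confidence level", and ±5% at 80% confidence, and calls this acceptable.

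Section 5.3.3.1 refers to more than one instrument: "Our goal is to assess the validity and reliability of the two PREMS". Section 5.2.1.1 and the appendices show what they are. PREM 1 (Appendix 8, Section 1) has 18 statements and is sent 2 weeks after discharge. PREM 2 (Appendix 9, Section 1) has 15 different statements and is sent at 3 months.

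On loss, section 4 says of the intervention sample: "but with attrition, we predict a smaller final sample size". Estimate A in 5.3.1 mentions attrition and supports 84 intervention participants by a cited finding that "70 measurable subjects are required when outcomes are continuous". The progression table in 5.3.3.2 rates loss to follow-up at 2 months as Green below 20% and Amber at 21-35%. It rates collection of outcome measures as Green above 75%.

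**The concern.** The span of 15 to 18 items reads as uncertainty about the length of one questionnaire, and 168 falls inside the resulting 150 to 180. In fact 15 and 18 are the lengths of two separate questionnaires, each to be validated on its own responses. For the longer one, 168 is below the protocol's own requirement before anyone is lost.

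The rule and the margin both concern returned answers, while 168 is the number recruited in hospital. Respondents are frail and aged 75 or over, and they reply weeks or months after discharge. Estimate C has no term for non-return.

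PREM validation is named with feasibility as the primary outcome (section 3.3), and section 1 presents the PREM as a candidate primary outcome for later trials. If C stands, the factor analysis and reliability results would be reported as resting on a response count that the design does not supply.

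Estimate A has a smaller gap. It relies on a figure for continuous outcomes, but the progression criteria it serves are a recruitment rate and percentages. It also does not say how much loss 84 can absorb.

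**Working it through.** **Inputs.** Recruits: 168 in total, 84 in the intervention arm (5.3.1). Rule: 10 responses per item (5.3.1). Items: 18 (Appendix 8) and 15 (Appendix 9). Measurable subjects: 70 (5.3.1 A).

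**1. The protocol's own figures.** The margin at proportion p with n responses is z × √(p(1−p)/n). With p = 0.5 and n = 168:
- 95%: 1.96 × √(0.25/168) = 7.56 points (stated 7.5).
- 80%: 1.2816 × √(0.25/168) = 4.94 points (stated 5).
- Rule: 15 × 10 = 150 and 18 × 10 = 180.

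All reproduce, apart from rounding.

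**2. Each PREM with no loss.**
- PREM 1: 168/18 = 9.33 per item, against 10. It needs 180, which is 12 more than are recruited.
- PREM 2: 168/15 = 11.2 per item. It needs 150, so the largest tolerable non-return is 1 − 150/168 = 10.7%.

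**3. Each PREM with non-return.** Returns = 168 × (1 − d). The protocol gives no expected d, so the rates below are assumptions. The loss criterion is set at 2 months, and neither PREM is collected then. The 25% row is the Green/Amber boundary for outcome collection, read as the share of participants who supply the measures; it does not depend on the 2-month timing.

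| Non-return d | Returns | PREM 1 per item | PREM 2 per item | 95% margin at p = 0.5 |
|---|---|---|---|---|
| 0% | 168 | 9.3 | 11.2 | ±7.6 |
| 20% | 134 | 7.5 | 9.0 | ±8.5 |
| 25% | 126 | 7.0 | 8.4 | ±8.7 |
| 35% | 109 | 6.1 | 7.3 | ±9.4 |

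Example at 20%: 168 × 0.80 = 134.4; 134.4/18 = 7.47; 134.4/15 = 8.96; 1.96 × √(0.25/134.4) = 8.45 points.

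**4. Estimate A.** The 70 is read as applying to the intervention arm, as the text uses it.
- Tolerable loss: 1 − 70/84 = 16.7%.
- At 20% loss: 84 × 0.80 = 67.2, about 67.
- At 35% loss: 84 × 0.65 = 54.6, about 55.

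Interval half-width for a progression proportion at n = 84, before any allowance for site clustering:
- p = 0.5: 1.96 × √(0.25/84) = 10.7 points.
- p = 0.2: 1.96 × √(0.16/84) = 8.6 points.

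**The case against.** Several points on the other side are sound.

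- **The margin is correct and conditional.** Section 5.3.1 offers it only if 168 is reached, and the arithmetic is right. At 20% non-return it widens by less than one point. A reader might infer that ±7.5% was miscalculated; it was not. What stands is that the condition requires a complete return which the plan nowhere expects.
- **The protocol prints 180 beside 168.** An attentive reader can see the shortfall, and 9.3 against 10 on a self-described rule of thumb is small. But the text presents a range for one instrument and does not say that its upper end is the requirement for PREM 1.
- **Estimate A does consider attrition.** A reader might infer that it too confuses recruits with measurable subjects. The document does not support that: 84 against 70 leaves room for 16.7% loss, which covers most of the Green band. The shortfall just under 20% is about three people. If the 70 were a total across both arms, 168 would satisfy it up to 1 − 70/168 = 58% loss.
- **The progression bands are not forecasts.** They judge whether a later trial is feasible, and the loss band is set at 2 months. It would be too strong to say that the response targets will be missed because 20% or 35% loss is coming. Loss may be lower at 2 weeks and higher at 3 months.
- **Clustering.** A reader might argue that eight hospitals make the margin wider still. The protocol gives no intraclass correlation, and clustered intervals can be left to an analysis plan, so this point does not rest on it.

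None of this removes the PREM 1 shortfall at zero loss or the missing allowance for non-return in C.

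**Conclusion.** Estimate C is wrong as written in two respects. It applies one item range to two instruments, so PREM 1 cannot meet the stated rule with 168 recruits under any return rate. It also equates recruits with responses, so PREM 2 meets the rule only up to 10.7% non-return and the ±7.5% margin holds only with none. These results need only the protocol's own counts. The figures at 20%, 25% and 35% are illustrations on assumed rates.

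Estimate A is incomplete rather than wrong about attrition. Its tolerance of 16.7% is unstated, and a continuous-outcome figure does not show how precisely proportions are estimated.

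Severity is moderate. A reader might infer that the sample is inadequate and must grow; holding ten per item at 20% non-return would take 150/0.80 = 188 recruits for PREM 2 and 180/0.80 = 225 for PREM 1. The document does not support that demand: the rule is a convention and this is a feasibility study with descriptive aims. What has to change is the claim made for 168.

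**What to change.** Keep 168 and revise section 5.3.1.

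- **Estimate C:** give separate entries for PREM 1 (18 items, 2 weeks) and PREM 2 (15 items, 3 months). For each, state the assumed return rate at that time point, the expected returns, the responses per item and the 95% margin. Say plainly that PREM 1 has at most 9.3 responses per item. If the team has no basis for one return rate, show a range such as the table above, labelled as assumed.
- **Estimate A:** state that 84 gives 70 measurable subjects up to 16.7% loss (67 at 20%), and whether 70 refers to the intervention arm. Add the interval half-width for a proportion at n = 84: about ±10.7 points at 50% and ±8.6 at 20%, before clustering.

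The 80%-confidence line may stay, since it is correct for n = 168, but it needs the same return-rate condition. No fixed intraclass correlation is required here.

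The cost is rewording and a less favourable statement of precision. Recruitment, sites, data collection and the planned analyses do not change.

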5.3.3.2 Analysis of the Intervention Outcome Measures

We shall focus on descriptive statistics such as percentages, means and standard deviations to understand the key features of the data from the outcome measures (Healthcare utilisation, Medicine-Related Problems, Self-efficacy, QoL, and Adherence) and the staff survey.

Criteria to determine if the intervention should proceed to RCT will be refined in agreement with our project advisory board. We will apply 'Red', 'Amber', and 'Green' (RAG) criteria (Young et al., 2019), which we have previously applied in our work (ISCOMAT programme RP-PG-0514-20009). Key criteria will be based on recruitment, intervention delivery, and participant engagement:

Criteria	Green	Amber	Red
Rate of recruitment	2 participants per week per site	1 participant per week per site	0 participant per week per site
Loss to follow up at 2 months	<20%	21-35%	>35%
Intervention delivery >50% on fidelity rating scale	100%	50-99%	<50%
Participant engagement with intervention (use of checklist, self-management plan and engages with DMS)	>75%	40-74%	<40%
Evidence of feasibility to collect outcome measures	>75%	35-75%	<35%

We will regularly review progress against the RAG progression criteria at project meetings and assess whether these are achievable within a full trial. Where progress is 'amber', barriers to implementation should be resolvable and we will work with our project advisory group (PAG) to review and adapt methods within the feasibility study. If more than 50% of our RAG criteria result in 'red' scores, we will not progress to a further full trial.

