	Strongly agree	Agree	Not sure	Disagree	Strongly disagree

My Me	edicines Journey:	Assessing the fe	easibility and imple	ementation of a To	olkit
	\bigcirc	\bigcirc	\bigcirc	\bigcirc	\bigcirc
10. (e		•	•	mmunity healt and understoo Disagree	
11. m	Someone had be dicined a strongly agree	s dealt with r	ny concerns a	nnd questions a Disagree	Strongly disagree
12.	I know how need to take. Strongly agree	Agree	Not sure	d am aware of Disagree	any actions I Strongly disagree
13. fro	I am able to com the pharma Strongly agree			need and can a	Strongly disagree

14. I feel supported by my family and friends or my social care team (e.g. carers) to manage my medicines at home if I want them to.

My Medicines Journey: Assessing the feasibility and implementation of a Toolkit Strongly Not sure Disagree Strongly Agree disagree agree I feel confident managing my medicines and need no further 15. support. Strongly Not sure Disagree Strongly Agree agree disagree ©Bradford Teaching Hospitals Trust **Section 2: About your medicines Instructions:** These next statements ask about any issues with your medicines. Read each statement. Mark if you have always, sometimes, or never experienced that problem in the last 2 weeks. 2. I have problems getting the medicines I need. Never **Always** Sometimes 3. I struggle to organise my medicines at home. Never Sometimes **Always** 4. I am not sure how to store my medicines. Never Sometimes Always

My Medicines Journey: Assess	sing the feasibility and implement	ation of a Toolkit
5. I am not sure how to	get rid of unwanted medic	cines.
Never	Sometimes	Always
\bigcirc	\bigcirc	\circ
6. I struggle to physical them).	ly take my medicines (e.g.	swallowing or injecting
Never	Sometimes	Always
		\bigcirc
7. I forget to take my		A .
Never	Sometimes	Always
O	\cup	\cup
8. I have problems plan	ning when to take my med	dicines.
Never	Sometimes	Always
\bigcirc	\bigcirc	\bigcirc
9. I do not know if my m	nedicines are working.	
Never	Sometimes	Always
_	_	_
10. I am not happy wi	th how my medicines affe	ct me.
Never	Sometimes	Always
\bigcup	\bigcup	\cup

My Medicines Journey: Assessing the feasibility and implementation of a Toolkit

11. e	I worry that takin ffects.	g medicines for a long time	may cause future side
	Never	Sometimes	Always
	\bigcirc	\bigcirc	\bigcirc
12.	I do not know if r	my medicines work well toge	ether.
	Never	Sometimes	Always
13.	Different healths	are professionals tell me difl	forant things about my

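### Protocol section 5.3.1, item C sizes two separately validated PREMs as one instrument and counts the 168 recruits as responses, so PREM 1 falls short of the protocol's own 10-per-item rule and the stated margins hold only with no loss

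*Protocol*

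**What the plan says.** Protocol section 5.3.1, item C rests the validation sample on a heuristic: "a widely used rule of thumb suggests 10 responses per item in the instrument". It continues: "The PREM contains 15 to 18 items, leading to a sample size in the range of 150 to 180", and then: "The intended sample size is 168". Provided that number is reached, it gives a margin of error per item of 7.5% at 95% confidence and 5% at 80% confidence, for a proportion of 50%, and calls this acceptable.

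The same section shows what the 168 are: "We plan to recruit a diverse sample of 168 older people across 4 intervention sites and 4 control sites during hospital admission". They are 84 intervention and 84 control participants.

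Section 5.3.3.1 refers to more than one instrument: "Our goal is to assess the validity and reliability of the two PREMS". Appendix 8, Section 1 (hospital stay and preparing to leave) runs to 18 statements. Appendix 9, Section 1 (experience at home) ends at statement 15, which begins "I feel confident managing my medicines and need no further". Section 5.2.1.1 places PREM 1 at 2 weeks and PREM 2 at 3 months after discharge.

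On attrition, section 4 says of the intervention participants: "but with attrition, we predict a smaller final sample size". The progression table in section 5.3.3.2 has a row headed "Loss to follow up at 2 months", with Green below 20% and Red above 35%. Item C itself makes no allowance for non-response.

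**The concern.** Two different things are merged in item C. First, the item range matches the two booklets: 15 is the printed length of PREM 2 and 18 that of PREM 1. The instruments differ in content and timing, and section 5.3.3.1 treats them as two, so each needs its own count. A single figure chosen from inside the range satisfies the shorter instrument and not the longer one.

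Second, the rule is expressed in responses, while 168 is a recruitment figure. The questionnaires come back by post, telephone or online, weeks to months after recruitment.

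PREM validation is the first-listed objective in section 3.1 and part of the primary outcome in section 3.3. Section 4 gives it as one reason for recruiting the control group, and section 1 describes the PREM as a candidate primary outcome for later trials. A reader of item C would take it that the chosen rule is met and that the quoted precision will be available for both instruments.

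**Working it through.** **Inputs.** 10 responses per item, 168 intended, and margins of 7.5% and 5% at a proportion of 50% (section 5.3.1, item C); 18 items for PREM 1 (Appendix 8, Section 1); 15 items for PREM 2 (Appendix 9, Section 1).

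**Step 1: reproduce the protocol's figures.**
- Rule: 15 × 10 = 150 and 18 × 10 = 180. Both agree.
- Margin = z × √(0.25/n). With n = 168: 1.96 × √(0.25/168) = 7.56% at 95%, and 1.2816 × √(0.25/168) = 4.94% at 80%. These agree with 7.5% and 5% to rounding, so the calculation uses all 168 as responders.

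**Step 2: apply the rule to each instrument with no loss.**
- PREM 1: 168/18 = 9.3 per item. Required 180; shortfall 180 − 168 = 12, or 12/180 = 6.7%.
- PREM 2: 168/15 = 11.2 per item. Required 150; the rule is met.

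**Step 3: loss that PREM 2 can bear.** 1 − 150/168 = 10.7%. Above that, PREM 2 also falls below 10 per item.

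**Step 4: responders instead of recruits.** The protocol states no expected loss at 2 weeks or at 3 months, so the loss rates below are assumptions. Responses n = 168 × (1 − loss), rounded to whole people; per-item figures are n/18 and n/15.

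| Assumed loss | Responses | PREM 1 per item | PREM 2 per item | Margin, 95% | Margin, 80% |
|---|---|---|---|---|---|
| 0% | 168 | 9.3 | 11.2 | 7.6% | 4.9% |
| 10% | 151 | 8.4 | 10.1 | 8.0% | 5.2% |
| 20% | 134 | 7.4 | 8.9 | 8.5% | 5.5% |
| 35% | 109 | 6.1 | 7.3 | 9.4% | 6.1% |

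The rows should be read separately for each PREM. Loss at 2 weeks may well be lower than at 3 months, so the two instruments need not sit on the same row.

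**The case against.** The strongest reply is that nothing is miscalculated or hidden. Item C prints 180 as the upper end and 168 as the intended number, and it calls the rule a rule of thumb, not a minimum. The margins are conditional on reaching 168, and the protocol says it finds them acceptable. PREM 1 at 9.3 per item is close to 10, and PREM 2 exceeds it. The set-up stage also includes refining the PREM, so the item count might fall; at 16 items the rule would ask for 160, and 168 complete responses would meet it.

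Much of this stands. The arithmetic is correct, the no-loss gap is small and concerns PREM 1 only, and the shortfall applies to the booklets as printed. Two parts do not answer the point. The condition attached to the margins refers to the intended 168, which is the recruitment number, so it does not cover non-response. And a single range for one PREM does not tell the reader that its upper end belongs to the instrument that misses the rule.

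A reader might also infer that the protocol expects 20% or 35% loss and so forecasts about 134 or 109 analysable questionnaires. The documents do not support that. Those limits are progression bands set at 2 months, a time point that matches neither PREM, and they are thresholds for judging feasibility, not expected rates. The sentence in section 4 about a smaller final sample concerns the intervention participants and gives no rate.

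**Conclusion.** The point holds in a limited form. Item C presents one size for two instruments and treats recruits as responses. For PREM 1 as printed, the 10-per-item rule is missed at any loss rate, by 12 responses at best. For PREM 2 it is met only if loss by 3 months is no more than 10.7%. The stated margins describe complete response; across the illustrated losses of up to 35%, the 95% margin widens from 7.6% to 9.4%, which is under 2 percentage points.

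The PREM 1 result with no loss rests only on the printed item count and the protocol's own rule. Everything beyond that depends on assumed loss.

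A reader might conclude that the validation cannot be carried out or that recruitment must rise. That does not follow: the rule is a heuristic, the gap with no loss is modest, loss of up to 10.7% still leaves PREM 2 at its target, and PREM validation is not one of the progression criteria. This should be corrected because the protocol relies on these figures for a primary objective, but it does not undermine the design.

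**What to change.** Rewrite item C of section 5.3.1 as follows:

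- State the requirement for each instrument: 180 responses for the 18-item PREM 1 at 2 weeks, and 150 for the 15-item PREM 2 at 3 months.
- Say that 168 is the number recruited, and report responders separately for each PREM.
- Replace the single pair of margins with responses per item and margins over a range of loss, such as the table above. Label the range as an assumption, because the protocol gives no expected loss at either time point and its progression limits apply at 2 months. Do not write any one loss rate in as an expectation.
- Acknowledge that the 10-per-item rule is not met for the 18-item PREM 1, and that its factor structure will be treated as provisional.
- If refinement changes the number of items, update the counts.

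The cost is protocol wording only. No extra recruitment, data collection or change to the progression rule is needed; the stated size and precision simply become less favourable.
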